8.2. Statistical analysis

The main hypotheses that will be tested in a hierachial fashion are:

- Combined treatment with VAR and BUP reduces blood concentrations of B-PEth from baseline and significantly more than double-placebo, VAR or BUP alone.
- VAR reduces B-PEth from baseline and significantly more than double-placebo.

The ANCOVA analysis will compare the mean values of the variable in question for the different treatment groups hierachially. Regulatory agency will consider only one specific primary objective and since the two primary endpoints fulfill regulatory requests independently and separately, no adjustment for multiplicity has been done. As testing between treatments are performed in a hierachial fashion, no adjustment for multiple testing has been done.

The SAS® software, version 9.2 or higher, will be used to produce all of the statistical outputs.

All efficacy and safety variables will be presented using descriptive statistics and graphs as appropriate.

Safety measures will be summarized descriptively using the safety analysis set. Continuous variables will be presented with descriptive statistics (n, mean, standard deviation [SD], median, min, max), within treatment group. Categorical variables will be summarized by treatment group in frequency tables (number of patients and percentage). The denominators for all percentages will be defined as the number of non-missing values for each variable within the analysis set. Percentages will be presented with 1 decimal place.

Primary efficacy variables

- **B-PEth**

One of the primary outcomes will be level of PEth measured in blood.

The primary efficacy variable, B-PEth, is calculated as the mean value over the 8-week steady state active treatment period visit 4 – visit 8 (Day21-Day77) compared to baseline. The data is analyzed as the within patient difference. Day78-Day91 is omitted in the analysis period due to the tendency of drop-out and non-compliance at the end of a study period. Day 0-Day21 is omitted in the analysis due to titration of IMP and optimal timeframe of B-PEth analysis.

Additionally, B-PEth-level analysis compared to baseline levels will also be performed for Day7, Day 21, Day 35, Day 49, Day 63 and Day 77. B-PEth has a well-documented declining pattern and hence it follows that the mean value during the treatment period will be a sufficient statistic for the post-treatment level. B-PEth will be collected initially at the screening visit and onwards from randomization visit every 2nd week during the study (except for the first visit, which is one week after randomization). An analysis with regards to B-PEth, will be performed using an analysis of covariance (ANCOVA) using the mean value of B-PEth (day21-day77) within patient, as the dependent variable. Adjustments for following covariates will be performed: treatment group, center, nicotine use (Yes/No) and family history positive, FHP (Yes/No).

The ANCOVA model will have fixed effects for treatment and center and subject, nicotine use and FHP will be entered as random effect.

Baseline B-PEth will be used as a covariate in the analysis.

- **Heavy Drinking Days (HDD)**

The additional main outcome will be alcohol consumption as measured by Heavy Drinking Days (HDD) using the Time Line Follow Back (TLFB) procedure. The number of heavy drinking days HDD by 14 days is defined as a mean over the 8-week steady state active treatment period (Day 21 -Day 77) compared to baseline. A HDD is defined in two ways; as ≥ 60 grams for men and ≥ 40 for women according to EMA's guideline and as ≥ 70 grams for men and ≥ 56 grams for women according to FDA's guideline on the development of medicinal products for the treatment of alcohol dependence. The baseline mean of heavy drinking days by 14 days, is obtained at the screening visit, where the number of heavy drinking days over the last 30 days is registered.

The number of heavy drinking days, "HDD 21-77", is the total number of heavy drinking days divided by 4 (8weeks/2), in order to get a 14 day-period measurement. The maximum total number of days measured is 56 days. Additionally, HDD analysis compared to baseline levels will also be performed for Day7, Day 21, Day 35, Day 49, Day 63 and Day 77 and parts of the 8 week steady state active treatment period.

Adjustment for the covariates treatment group, smoking (Yes/No), family history positive, FHP, (Yes/No) and center will be performed. Baseline alcohol consumption will be used as a covariate in the analysis. The

ANCOVA model will have fixed effects for treatment and center and subject, nicotine use and FHP will be entered as random effect.

Definition of analysis sets

Three analysis sets will be used: Modified Intention-To-Treat (mITT), Per Protocol (PP) and Safety. The primary and secondary efficacy endpoints will be estimated using ITT and PP analysis sets separately. The safety endpoints will be analyzed on the safety analysis set.

1) Modified Intention-to-treat (mITT) analysis set

The mITT analysis set will include all trial subjects who complete screening visit and randomization visit and report that they have taken at least one dose of the randomized IMPs. Subjects will be analyzed according to their randomized IMPs.

2) Per-protocol (PP) analysis set

The PP analysis set constitutes all subjects from the ITT population who are considered to be completers. A completer is defined as a subject who:

- has taken the IMP at least 80% of the planned number of days of the active treatment period
- fulfill the visit milestones, where the visit milestones are met by subjects who have:
 - taken part and completed screening visit, Day 0, Day 21, Day 49 and Day 77
 - successful B-PEth analyses at screening visit, Day 0, Day, 21, Day 49 and Day 77
 - completed TLFB data at screening visit, Day 0, Day, 21, Day 49 and Day 77

In case of violation of any of the above-mentioned criteria the subject will not be included in the PP analysis set for the specific outcome variable. Subjects will be analyzed according to their randomized study drug.

3) Safety set

The safety analysis set includes all subjects who report that they have taken at least one dose of randomized study drug, and for whom any post-dose data is available up until Day 77. Patients will be analyzed according to the actual treatment.

Compliance

Adherence to the study drug regimen will be analyzed by pill count and by plasma levels of IMP1 and IMP2 at visit 4 and visit 6.

Randomization issues

Mistakenly randomizing a subject who does not meet the inclusion/exclusion criteria will be considered a protocol violation. Any such subject will not be included in the analysis sets.

Handling of missing data

Handling of missing data in the alcohol consumption data as measured by TLFB. In a blind data review, missing data will be assessed. If found appropriate, since we expect that the missing data are not at random, due to the tendency of alcohol patients to have a drinking pattern, we will handle the missing data not by last observation carried forward (LOCF), but instead by an imputation taking the subjects pattern into account. The missing day will be imputed by the data from the same weekday in the weeks before and after, if possible. To adjust for changes in alcohol consumption over time, the weeks closest to the missing day will have a greater weight than the weeks more distant from the missing day.

If a subject drops out from the study in early treatment, the baseline observation will be carried forward. If the subject drops out late in the treatment period the last observed 7 days will be carried forward, if there are missing days, these will be imputed as described above. This model allows for the probability that a longer treatment period will have a greater impact on the alcohol consumption. For all other variables missing data will be considered missing and no imputation will be computed.

All statistical concerns and estimations are described in a separate statistical protocol, the Statistical Analysis Plan (SAP).

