1.2. Risk-Benefit Evaluation

This section gives risk-benefit evaluation for the conductance of the trial and for the use of VAR in the dose of 1 mg x 2 daily and BUP in the dose of 150 mg x 2 daily, in combination and alone.

Clinical and ethical standards

To give the best conditions possible for the safety of the study subject, the trial will be conducted in compliance with the ethical principles that have their origin in the Declaration of Helsinki and with the ICH Good Clinical Practice (GCP) guidelines.

Anticipated clinical benefits with VAR and BUP and B-PEth as used in the study

- The main benefit of the present study would be showing a superior treatment effect of the combination of drugs VAR and BUP, compared to VAR alone in AUD, which would be a first time finding. Further, if the effect size is 0.5-0.6 (Cohen's d), as hypothesized, this would represent the largest effect size observed for any available treatment of AUD.
- A second benefit would be confirming the treatment effect of VAR on alcohol consumption in AUD patients, which would represent the third study showing this effect.
- A third benefit would be showing a significant treatment effect of BUP on alcohol consumption in AUD patients, which would be a first time ever finding.
- A fourth benefit would be to demonstrate the superiority of B-PEth over self-report (in this case TLFB) for disclosing treatment effects in a second alcohol treatment trial. Such a finding may contribute to changing and improving the standards regarding primary outcome variables in alcohol treatment trials.
- A fifth benefit would be for the health care. Assessing the utility of B-PEth as biomarker will help clinicians screen for alcohol problems in a reliable fashion.

Health economic benefits

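### Sections 8.1, 3.2 and 8.2 disagree on the confirmatory hypotheses: the 8.2 hierarchy omits BUP versus placebo and puts unsized combination-versus-single-drug tests ahead of VAR versus placebo

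*Protocol*

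**What the plan says.** Protocol 8.2 lists two main hypotheses for hierarchical testing, both on B-PEth. The first is "Combined treatment with VAR and BUP reduces blood concentrations of B-PEth from baseline and significantly more than double-placebo, VAR or BUP alone". The second, and last, is "VAR reduces B-PEth from baseline and significantly more than double-placebo". The section then states "The ANCOVA analysis will compare the mean values of the variable in question for the different treatment groups hierachially" and concludes "As testing between treatments are performed in a hierachial fashion, no adjustment for multiple testing has been done". No other reason is given for leaving the treatment contrasts unadjusted.

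Other sections name a different set:

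- **8.1** bases the power analysis on two primary hypotheses, one for B-PEth and one for HDD. In each, the combination, VAR alone and BUP alone are compared with placebo. No comparison of the combination with a single drug appears.
- **3.2** gives three design hypotheses: combination, BUP and VAR, each against placebo. The hypothesised B-PEth effects are d 0.5–0.6, about 0.35 and about 0.35.
- **1.2** names as the main benefit a "superior treatment effect of the combination of drugs VAR and BUP, compared to VAR alone in AUD". It continues with "A second benefit would be confirming the treatment effect of VAR on alcohol consumption in AUD patients" and "A third benefit would be showing a significant treatment effect of BUP on alcohol consumption in AUD patients".

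**The concern.** BUP versus placebo belongs to the primary hypotheses in 8.1 and is a design hypothesis in 3.2, yet it has no place in the 8.2 list. Combination versus VAR and combination versus BUP stand in the first item of 8.2, although 8.1 does not size them. VAR versus placebo, which 8.1 does name, comes after them.

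Item 1 also joins three contrasts without saying what must succeed before item 2 is opened. Because the hierarchy is the whole argument against adjustment, the pass rule decides both the error rate and the chance of a confirmatory VAR result. At stake is whether the trial can deliver the second and third benefits named in 1.2, and whether a rule settled after unblinding would be believed.

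**Working it through.** **Step 1. Reproduce 8.1 and infer the sidedness.** Inputs from 8.1: α = 0.025, power 0.80, SD 0.8 with 80 per arm (B-PEth), SD 0.35 with 90 per arm (HDD). Sidedness is not stated. Normal approximation: detectable d = (z_α + z_power) × √(2/n).

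| Reading of 0.025 | B-PEth, n = 80 | HDD, n = 90 |
|---|---|---|
| One-sided (1.960 + 0.842) | d 0.443, difference 0.354 | d 0.418, difference 0.146 |
| Two-sided (2.241 + 0.842) | d 0.487, difference 0.390 | d 0.460, difference 0.161 |
| Printed in 8.1 | d 0.44, difference 0.35 | d 0.43, difference 15% |

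The printed figures fit one-sided 0.025 (0.35/0.8 = 0.44; 0.15/0.35 = 0.43). I use that reading, with the 90 per arm that 8.1 targets for the modified ITT set.

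**Step 2. Effects.** Placebo 0, VAR 0.35, BUP 0.35, combination 0.5–0.6 SD (3.2). Assuming a common SD, combination versus a single drug is 0.5 − 0.35 = 0.15 to 0.6 − 0.35 = 0.25.

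**Step 3. Single contrasts.** Power = Φ(d√(n/2) − 1.960), with √45 = 6.708.

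| Contrast | d | Power |
|---|---|---|
| Combination vs placebo | 0.50–0.60 | 92–98% |
| VAR vs placebo | 0.35 | 65% |
| Combination vs VAR (or BUP) | 0.15–0.25 | 17–39% |

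**Step 4. Readings of the hierarchy.** The contrasts share arms, so I simulated four independent arm means (2,000,000 draws, known SD, no covariate gain). The last column is the chance, when no treatment works, that item 1 is declared in favour of the combination.

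| What opens VAR vs placebo | Gate passes | VAR reached and won | Item-1 error |
|---|---|---|---|
| All three contrasts | 7–23% | 3–12% | 0.2% |
| Strict order as listed | 7–23% | 3–12% | 2.5% (first test) |
| Combination vs placebo alone | 92–98% | 63–65% | 2.5% |
| Any one of the three | 92–98% | 63–65% | 6.3% |

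**Step 5. Sensitivity.** Section 8.2 says "Baseline B-PEth will be used as a covariate in the analysis", which raises power. The protocol gives no baseline correlation ρ, so the values below are assumptions; each d is divided by √(1 − ρ²).

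| ρ | Combination vs VAR | VAR tested directly | VAR behind all three |
|---|---|---|---|
| 0 | 17–39% | 65% | 3–12% |
| 0.5 | 21–49% | 77% | 6–22% |
| 0.7 | 29–65% | 91% | 13–44% |

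At combination d 0.6 the all-three gate keeps 48% of VAR's direct power at ρ = 0.70, 57% at 0.75 and 68% at 0.80. If 0.025 is two-sided and ρ = 0, VAR tested directly has 54%, and behind all three 1–5%.

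**The case against.** The strongest reply is that item 1 has a natural meaning: more than each of the three comparators. On that reading, or as a strict sequence, the plan can be run, error within B-PEth is controlled and no adjustment is needed. This stands. A reader might infer that the hierarchy cannot be carried out, or that it inflates type I error; the text supports neither. Inflation arises only if any one contrast suffices, which is a less natural reading of the sentence.

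It can also be said that the order and pass rule inside item 1 belong in the SAP, to which 8.2 refers and which is not at hand. That is fair for the pass rule. It does not answer the mismatch: a SAP can add detail, but 8.1 and 8.2 would still name different hypotheses.

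A sponsor may also choose to leave BUP versus placebo outside the confirmatory set, and 1.2 and 3.2 are narrative and rationale rather than a definition of that set. Both are true. But 8.1 calls the comparison primary, and nothing in 8.2 says that it was dropped on purpose.

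Finally, the low power of combination versus VAR is a sample-size matter. No ordering cures it: 80% power needs about 253 per arm at d 0.25 and 699 at d 0.15.

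**Conclusion.** The concern holds as a contradiction over which hypotheses are confirmatory, with a cost in power and not in type I error. The 8.2 list omits BUP versus placebo, which 8.1 and 3.2 include, and adds combination versus each single drug, which 8.1 does not size. On the natural reading, VAR versus placebo is reached and won in 3–12% of trials, against 65% tested directly. This assumes 90 per arm, one-sided 0.025, the effects in 3.2, a common SD and no covariate gain.

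A reader might also infer that the gate always costs VAR at least half its power. That is true at the correlations of 0, 0.5 and 0.7 shown, but not above about 0.7 when the combination effect is 0.6, and the protocol gives no correlation. The mismatch itself does not depend on these figures. It should be fixed; in a phase II trial with a remedy in the text alone, it is not fatal.

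**What to change.** Before unblinding, replace the two items in 8.2 with one fixed sequence of single contrasts that starts with combination versus placebo and includes BUP versus placebo. State the level and its sidedness. Say that the same sequence applies separately to HDD, since both items now name only B-PEth.

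The position of combination versus VAR is the sponsor's choice, because 1.2 calls it the main benefit. Two possible orders, under the assumptions of step 4:

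| Won as confirmatory | Placebo contrasts first (combination, VAR, BUP), then combination vs VAR, then vs BUP | Combination vs VAR second, then VAR, BUP vs placebo |
|---|---|---|
| VAR vs placebo | 63–65% | 6–18% |
| BUP vs placebo | about 49% | 5–15% |
| Combination vs VAR | 5–15% | 17–39% |

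For comparison, the joint claim of item 1 as now written succeeds in 7–23%. If combination versus VAR stays ahead, the protocol should say that VAR and BUP versus placebo are then unlikely to be confirmatory. If BUP versus placebo is left out on purpose, say so and align 1.2, 3.2 and 8.1.

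The change needs no patients and no new data. Its cost is the trade between objectives shown in the table.

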Varenicline (VAR) is a registered smoking cessation medication that by its partial agonistic effect at brain nicotinic acetylcholine receptors (nAChRs) slightly elevates brain dopamine (DA) levels. VAR has been shown to reduce alcohol intake in two randomized controlled trials (RCTs). One was performed by the Sponsor/PI with the Swedish Network for Treatment Trials in the Addiction Field (de Bejczy et al., 2015) and one was performed in the US, in a National Institute on Alcohol Abuse and Alcoholism (NIAAA) program for repurposing existent drugs for use in the treatment of AUD (Litten et al., 2013). The effect size was approx. 0.35 (Cohen's d) in the Swedish study and 0.4 (Cohen's d) in the American study. If confirmed in further trials this compound may thus outperform the drugs currently available for treatment of AUD.

Bupropion (BUP) is a centrally active, weak norepinephrine-dopamine reuptake inhibitor (NDRI) with minimal affinity to the serotonin transporter (Jorenby et al., 1999). It was registered for major depression in the 1980s (Voxra®, patent time expired), and based on clinical observations and a series of positive RCTs, BUP received approval as smoking cessation medication in 1997 (Zyban®, patent time expired). BUP is also being used off-label as treatment for attention deficit hyperactivity disorder (Kornfield et al., 2013) and the combination bupropion and naltrexone (Mysimba®) was registered September 2014 for the treatment of obesity. The hypothesis of the present study is that BUP will show a similar effect size as VAR for AUD, and that an effect size of 0.5-0.6 (Cohen's d) might be reached by combining VAR and BUP.

B-PEth is a validated biomarker for alcohol consumption and has superior sensitivity and specificity (theoretically 100%) compared to CDT and GGT (See Section 3.4 Study Assessments). It has been shown that B-PEth has high enough fidelity in AUD studies to pick up a treatment effect that CDT, GGT and self-report in a diary fail to disclose (de Bejczy et al., 2015). This will be the first study using the biomarker B-

PEth for alcohol intake as primary outcome variable. The aim of using a specific objective marker is to increase chances for detecting treatment effects and pave the way for future study guidelines in AUD. Self-reported heavy drinking days, the conventional effect measure for clinical trials in AUD, will be used as a separate primary outcome variable.

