2. STUDY OBJECTIVES AND ENDPOINTS

2.1. Primary objective

To assess the effects of VAR and BUP in combination and alone for reducing alcohol consumption in individuals with AUD.

Two primary efficacy end-points will be used.

- 1) Alcohol consumption as measured by the objective alcohol marker B-PEth
- 2) Alcohol consumption as measured by heavy drinking days (HDD*) by using the Time Line Follow Back (TLFB) procedure

*HDD is defined as ≥ 60 grams for men and ≥ 40 for women according to EMA's guideline and as ≥ 70 grams for men and ≥ 56 grams for women according to FDA's guideline on the development of medicinal products for the treatment of alcohol dependence.

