3.2. Rationale for study design

This trial assesses the efficacy of the established smoking cessation agents, VAR and BUP, on the new indication, AUD. The study assesses VAR and BUP alone and in combination, and is designed with 4 parallel groups to address the following hypotheses:

- Combination treatment with VAR and BUP reduces B-PEth levels and HDD from baseline and significantly more than placebo. The effect size, as measured by B-PEth, for the combined treatment is hypothesized to be 0.5-0.6 (Cohen's d).
- BUP reduces B-PEth levels from baseline and HDD from baseline and significantly more than placebo. The effect size, as measured by B-PEth, is hypothesized to be approximately 0.35 (Cohen's d).
- VAR reduces B-PEth levels from baseline and HDD significantly more than placebo. The effect size, as measured by B-PEth, is expected to be approximately 0.35 (Cohen's d).

Rationale for two primary End Points

Regulatory agencies will consider only one specific primary objective. The two primary endpoints fulfill regulatory requests independently and separately. HDD fulfill requirements for application of marketing approval. The biological marker is used to assess the reliability of PEth as End Point measure.

Rationale for the study design

A parallel group design will be used. A crossover design is not an option due to the risk that the beneficial effects of the first treatment will carry over into the second treatment period. The duration of a parallel-group trial is often shorter because only one treatment period is involved (yet a larger study group is needed). As in [name] et al. (de Bejczy et al., 2015) and Litten et al. (Litten et al., 2013) it is estimated that 12 weeks steady state duration will be adequate for detecting tentative effects, as measured by B-PEth and HDD, and at the same time be manageable for the participants, thus optimizing study compliance.

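### Section 8.2 tests two primary endpoints of one objective without adjustment and does not name the one that decides a primary claim

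*Protocol*

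**What the plan says.** Section 2.1 gives one primary objective, reducing alcohol consumption, and adds: "Two primary efficacy end-points will be used". These are B-PEth and HDD. Section 1 says of HDD that it "will be used as a separate primary outcome variable", and Section 8.1 sizes the trial for each endpoint as an independent primary hypothesis.

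On multiplicity between endpoints, Section 8.2 states: "since the two primary endpoints fulfill regulatory requests independently and separately, no adjustment for multiplicity has been done". The premise appears in Section 3.2: "Regulatory agencies will consider only one specific primary objective".

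The signals about which endpoint leads point in different directions:

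- Section 8.2 leans to B-PEth: "The primary efficacy variable, B-PEth, is calculated as the mean value".
- Section 8.2 introduces the other endpoint with less weight: "The additional main outcome will be alcohol consumption as measured by Heavy Drinking Days (HDD".
- Section 3.2 leans to HDD for licensing, "HDD fulfill requirements for application of marketing approval", and gives B-PEth the role of testing PEth as an endpoint measure.

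The hypotheses bulleted in Section 8.2 for hierarchical testing mention B-PEth only. The second, for example, reads "VAR reduces B-PEth from baseline and significantly more than double-placebo".

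**The concern.** The argument that an agency weighs only one primary objective is sound when the deciding endpoint is fixed before the data are seen. The other endpoint then cannot rescue a failed trial. Here both endpoints serve the same objective, both are called primary, and no sentence says whether one is enough, whether both are needed, or which one decides. A significant result on either could be reported as a positive primary outcome, and the error rate of such a claim exceeds the level used for sizing.

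Section 3.2 does not close the gap. It explains why each endpoint was chosen, but it does not say how a claim follows from the two tests.

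**Working it through.** **Step 1. Is the 0.025 in Section 8.1 already a split?**

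Inputs from Section 8.1: alpha 0.025 (sidedness not stated), power 0.80. B-PEth: SD 0.8, 80 per arm, stated effect 0.35 µmol/L (d = 0.35/0.8 = 0.4375). HDD: SD 0.35, 90 per arm, stated effect 15% (d = 0.15/0.35 = 0.4286).

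Detectable d, normal approximation: (z for alpha + 0.842) × √(2/n).

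- B-PEth, one-sided 0.025: (1.960 + 0.842) × √(2/80) = 0.443, times 0.8 = 0.354 µmol/L. With the t distribution: 0.357.
- B-PEth, two-sided 0.025: (2.241 + 0.842) × √(2/80) = 0.488, times 0.8 = 0.390 µmol/L. With t: 0.393.
- HDD, one-sided 0.025: 2.802 × √(2/90) = 0.418, times 0.35 = 14.6%. With t: 14.7%.
- HDD, two-sided 0.025: 3.083 × √(2/90) = 0.460, times 0.35 = 16.1%. With t: 16.2%.

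The stated 0.35 µmol/L and 15% fit one-sided 0.025, which is two-sided 5% for each endpoint. They do not fit a 5% level divided by two.

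**Step 2. Error if either endpoint can carry the claim.**

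For one treatment comparison with no true effect on either endpoint and one-sided 0.025 per test, the chance of at least one false benefit at correlation 0 is 1 − 0.975² = 0.0494. For positive correlations it comes from the bivariate normal distribution:

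| Assumed correlation | At least one false benefit | Multiple of 2.5% |
|---|---|---|
| 0 | 4.9% | 2.0 |
| 0.5 | 4.5% | 1.8 |
| 0.7 | 4.2% | 1.7 |
| 0.9 | 3.5% | 1.4 |

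Sections 1.1 and 3.4 indicate a positive correlation between B-PEth and reported intake but give no value, so the range is an assumption.

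**Step 3. Power after a split, 90 per arm.**

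Power ≈ Φ(d × √(n/2) − z), with √45 = 6.708.

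- B-PEth: 0.4375 × 6.708 = 2.935. Two-sided 5%: Φ(0.975) = 0.835 (t: 0.831). Two-sided 2.5%: Φ(0.694) = 0.756 (t: 0.749).
- HDD: 0.4286 × 6.708 = 2.875. Two-sided 5%: Φ(0.915) = 0.820 (t: 0.816). Two-sided 2.5%: Φ(0.634) = 0.737 (t: 0.730).

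Detectable effects at two-sided 2.5% and 90 per arm, with t: 0.463 × 0.8 = 0.370 µmol/L and 0.463 × 0.35 = 16.2%.

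**Step 4. Success on both endpoints under a fixed order.**

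Combination versus placebo at the B-PEth effect sizes in Section 3.2 (d = 0.5 to 0.6), 90 per arm, two-sided 5%, correlation 0 to 0.7. At correlation 0 with equal d = 0.5: Φ(0.5 × 6.708 − 1.960) = 0.918, and 0.918² = 0.84. The protocol gives effect sizes by B-PEth only, so the effect on HDD is an assumption:

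| HDD effect relative to B-PEth | Success on both |
|---|---|
| same d | 84–97% |
| 70% of it | 60–80% |
| half of it | 36–52% |

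**The case against.** **The hierarchy may cover HDD.** From the bullets alone a reader might infer that HDD has no place in the hierarchy. The documents do not support going that far. Section 8.2 applies the hierarchical ANCOVA to whichever variable is being analysed, and it specifies an ANCOVA for HDD as well. The objection stands to that extent. It does not remove the problem, because the result is two parallel hierarchies, each at full level, with nothing linking the endpoints. A reader might also think it open whether HDD counts once B-PEth has failed. The wording on independent and separate endpoints suggests that it does count, which is the situation in Step 2.

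**Two purposes, two claims.** This is the strongest defence. Section 3.2 assigns HDD to licensing and B-PEth to the question of PEth as a measure. If these are separate claims, each has its own error rate, and 3.5–4.9% describes a combined claim that the protocol never writes out. That is a fair reading, but it is not fixed as a rule. Both endpoints sit under one efficacy objective in Section 2.1, Section 1.1 argues that B-PEth should be the primary effect variable, and nothing prevents success on one from being reported as success of the trial.

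**The 0.025 looks like a split.** Step 1 rules this out for the sizing figures, and Section 8.2 itself says that no adjustment is made.

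**Phase II, and an SAP not shown.** An SAP may state the sidedness of the tests or which HDD threshold serves which agency, and neither is pressed here. The absence of adjustment, with its reason, is a rule that the protocol itself sets.

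**Conclusion.** The point holds. The protocol states a no-adjustment rule whose justification works only if the deciding endpoint is fixed in advance, and it does not fix it. If either endpoint can carry a positive primary claim, the false-benefit rate per treatment comparison is 3.5–4.9% against 2.5%, that is 1.4 to 2.0 times.

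This rests on three assumptions: each endpoint is tested at one-sided 0.025, the level that reproduces Section 8.1; the correlation lies between 0 and 0.9; and a claim may rest on either endpoint. If the tests were instead run at two-sided 0.025, the rate would be 1.8–2.5% and nothing would be inflated.

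A reader might infer that inflation is certain, or that the treatment comparisons themselves are uncontrolled. The documents do not support either. The gap is the missing rule between the two endpoints, and its effect depends on how a claim is made.

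**What to change.** Before unblinding, replace the no-adjustment sentence in Section 8.2 with one of the following.

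- **(a) Fixed order.** Name the endpoint that decides the primary claim and say when the other is tested. The first test loses no power, but the second endpoint then depends on the first. The order within the treatment hierarchy also matters. If HDD must succeed before later B-PEth comparisons, Step 4 shows how often it could block them should the HDD effect be smaller. If HDD instead waits for every B-PEth comparison, and combination versus varenicline is one of the gates, that gate alone passes in only 17–39% of trials: d = 0.15 to 0.25, Φ(0.15 × 6.708 − 1.960) = 0.17 and Φ(0.25 × 6.708 − 1.960) = 0.39. The protocol does not settle whether it is a gate.
- **(b) Split.** Run the hierarchy on each endpoint at two-sided 2.5%. Restate Section 8.1 as about 75% power for 0.35 µmol/L and 73% for 15% at 90 per arm, or as detectable effects of about 0.37 µmol/L and 16%. Keeping 80% on both endpoints would need 105 per arm analysed, 420 in total. That is about 443 randomised at the protocol's 360/380 ratio, or 449 at its 6.5% loss, instead of 380.
- **(c) Two separate claims, if that is the intention.** State which endpoint decides each claim, and that success on one will not be reported as success on the other.

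Options (a) and (c) need only a change of wording. Option (b) also costs the power shown, or the additional patients.
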